
Subjects who have been dose reduced will have an option to re-escalate to higher dose levels within their assigned dose cohort once the adverse event has resolved to grade 1 or less for at least 7 days. (See [Appendix F](#)).

Re-start of the infusion should be performed in the hospital, under supervision of the investigator. Before blinatumomab is re-started, premedication with dexamethasone must be administered as described in [Table 6-4](#). The subject should be observed overnight for possible side effects after each restart, either in the hospital or in the outpatient setting, as applicable. When the blinatumomab infusion is re-started per [Table 6-1](#) guidelines, the schedule of assessment procedures should be repeated to align with the re-started blinatumomab dose. If re-start is at 9 µg/d then repeat schedule of assessments starting at D1. If re-start is at 28 µg/d then repeat schedule of assessments starting at D8. Refer to [Table 7-1](#) and [Table 7-2](#) for cohort Ia and [Table 7-3](#) and [Table 7-4](#) for cohort IIa/IIIa. In addition, at the start of blinatumomab cycle 2, subjects should resume the schedule of assessments following D85 to D110 procedures as outlined in [Table 7-1](#) for cohort Ia and [Table 7-3](#) for cohort IIa/IIIa (exception is for pembrolizumab specific tests which are referenced in [Table 7-2](#) and [Table 7-4](#)).

In addition to the events described above, the dose may be temporarily or permanently reduced if, by investigator's judgment, it is necessary for safety reasons.

After at least 7 days of dosing at the reduced level, the dose may be increased back to the next higher dose level. An infusion interruption of more than 14 days due to an adverse event related to blinatumomab will lead to permanent discontinuation of treatment. In case of logistical difficulties, restart of treatment can be postponed for up to 7 additional days without resulting in permanent treatment discontinuation. Treatment may be also interrupted or permanently discontinued at the discretion of the investigator if any clinical/laboratory adverse event is considered to be medically relevant.

In case of signs of cytokine release, dexamethasone must be administered orally or IV at a dose of at maximum 3 x 8 mg/day for up to 72 hours.

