6.2.2.1 Pembrolizumab Dosage, Administration, and Schedule

Trial treatment should begin as close as possible to the date on which the subject is allocated/assigned. The pembrolizumab treatment to be used in this trial is outlined below in [Table 6-2](#).

Schedule of pembrolizumab dosing and related assessments for cohort Ia are provided in [Table 7-1](#) and [Table 7-2](#), and for cohorts IIa and IIIa are provided in [Table 7-3](#) and [Table 7-4](#). Pembrolizumab will be administered as a dose of 200 mg using a 30-minute IV infusion. Sites should make every effort to target infusion timing to be as close to 30 minutes as possible. However, given the variability of infusion pumps from site to site, a window between - 5 minutes and + 10 minutes is permitted (ie, infusion time is 30 minutes - 5 minutes/+ 10 minutes).

For this trial, an overdose of pembrolizumab will be defined as ≥ 1000 mg (5 times the dose) of pembrolizumab. No specific information is available on the treatment of overdose of pembrolizumab. In the event of overdose of pembrolizumab, the subject should be observed closely for signs of toxicity. Appropriate supportive treatment should be provided if clinically indicated.

Table 6-2. Trial Treatment

Drug	Dose/ Potency	Dose Frequency	Maximum Length of Dosing	Route of Administration	Regimen ^a	Use
Pembrolizumab	200 mg	Every 21 days	Up to 35 cycles	Intravenous	First dose starting at study day 15 (cohort Ia), and study day 19 (cohorts IIa and IIIa) (21-day cycles)	Experimental

^a Starting from pembrolizumab cycle 2, pembrolizumab may be administered ± 3 days from the planned dosing day.

6.2.2.2 Dosage Adjustments, Delays, Rules for Withholding or Restarting, Permanent Discontinuation for Pembrolizumab

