- The subject did not experience a DLT and completed the DLT **evaluation** period.

Duration of Blinatumomab/Pembrolizumab

Blinatumomab/ Pembrolizumab: For each infusion episode within a cycle, the duration of exposure will be calculated by subtracting the start date and time from the stop date and time. If either a start or stop time is missing, only the date portion will be used in calculating the duration of a specific infusion. For each cycle, the duration will be last date minus first date plus 1 of infusion. For the entire study, the duration will be the sum of the durations across cycles. The duration will be rounded to the nearest day.

Event of Clinical Interest (ECI)

Selected non-serious and serious adverse events are known as ECI and must be reported within 24 hours to the sponsor. The ECI for this trial includes

- An overdose of blinatumomab or pembrolizumab (see Protocol Section 6.2.1.1 and Section 6.2.2.1)
- Hepatic disorder (See protocol section 9.1.4)

Events of interest (EOI)

Events of interest (EOI) will be based on search strategies defined by Standard MedDRA Queries (SMQs) or Amgen MedDRA Queries (AMQs).

End of Investigational Product (IP) Administration Date

End of IP Administration for subjects who had blinatumomab or pembrolizumab is defined as the last infusion of blinatumomab/ pembrolizumab reported on the End of IP Administration CRF.

Enrollment Date

Enrollment Date is defined as the date of enrollment collected on the CRF.

Investigational Product

Amgen Investigational Product: refers to blinatumomab

Non-Amgen Investigational Product: refers to pembrolizumab

Last Dose Date of Blinatumomab/ Pembrolizumab

This is the stop date of the last infusion of blinatumomab/pembrolizumab administration reported on the Investigational Product Administration CRF.

Treatment period

Treatment period will be from study day 1 to 30 days after last dose of either blinatumomab/ pembrolizumab administration reported on the Investigational Product Administration CRF.

Prior Salvage Regimens

Prior salvage regimens are those medications recorded on the prior anti-cancer therapies CRF where the line of therapy field indicates 2nd or higher line therapy.

Relative Dose Intensity at the Target Dose

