10.6.8 Exposure to Investigational Product

Descriptive statistics will be produced to describe the exposure to blinatumomab and pembrolizumab. The number of cycles initiated, completed, discontinued, and re-started of blinatumomab and pembrolizumab will be summarized. **If a subject completed 85% of planned days on target dose, he/she is considered as completing a cycle.** In addition, the duration of therapy will be summarized by cycle and overall. **Relative dose intensity at the target dose will be calculated. It is the actual exposure duration at target dose divided by planned duration of target dose, which is 49 days for cohort Ia, and 42 days for cohort IIa and IIIa in cycle 1; and 21 days for cohort Ia, and 14 days for cohort IIa and IIIa in cycle 2. Subjects who didn't reach the target dose are considered having actual exposure duration as 0. Relative dose intensity at the target dose will be summarized by cycle.** The number and percent of subjects with dose modifications (eg, dose changes, dose interruptions) and reasons for modification will be summarized. **Analysis will be performed based on Safety Analysis Set.**

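### The SAP's duration rule makes pembrolizumab duration of therapy a count of infusions (35 days at 35 cycles, against a 715-day dosing span); the blinatumomab figure needs only a clearer label

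*SAP*

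**What the plan says.** SAP 6.1 has one entry on duration, headed for both drugs. It works at three levels:

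- **Infusion episode:** "the duration of exposure will be calculated by subtracting the start date and time from the stop date and time".
- **Cycle:** "For each cycle, the duration will be last date minus first date plus 1 of infusion".
- **Study:** "For the entire study, the duration will be the sum of the durations across cycles".

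It closes with "The duration will be rounded to the nearest day". SAP 10.6.8, in a paragraph that covers both drugs, then plans that "the duration of therapy will be summarized by cycle and overall". Neither section gives pembrolizumab its own rule or removes off-infusion days from the cycle figure.

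The two drugs are given very differently. Protocol 6.2.2.1 states "Pembrolizumab will be administered as a dose of 200 mg using a 30-minute IV infusion", and Table 6-2 sets this at one dose every 21 days for up to 35 cycles. Blinatumomab cycle 1 is a 56-day continuous infusion (Protocol 6.2.1.1) that may be interrupted and restarted. Protocol 6.2.1.4.1 sets a limit: "An infusion interruption of more than 14 days due to an adverse event related to blinatumomab will lead to permanent discontinuation of treatment", with up to 7 further days allowed for logistical difficulty.

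**The concern.** A last-minus-first rule within a cycle suits a drug infused over weeks. For a drug given once per cycle on one day it returns the constant 1. The by-cycle pembrolizumab row would read 1 day for every normally dosed subject, and the overall row would repeat the cycle counts that SAP 10.6.8 already tabulates. A reader of the study report who saw a pembrolizumab duration of therapy of a few days would be misled about how long subjects stayed on the drug.

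For blinatumomab the question is what the number means. The entry first defines a date-and-time duration of exposure per episode, then builds the cycle figure from calendar dates. Under one shared heading, the cycle figure could be taken for time actually on infusion.

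**Working it through.** **Inputs**

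- Duration rule: SAP 6.1, as quoted above.
- Pembrolizumab: one 30-minute infusion per 21-day cycle, at most 35 cycles, first dose on day 15 (cohort Ia) or day 19 (cohorts IIa and IIIa) (Protocol 6.2.2.1, Table 6-2).
- Blinatumomab cycle 1: 56 infusion days (Protocol 6.2.1.1), shown in Tables 7-1 and 7-3 as days 1 to 57.
- Interruption: up to 14 days for a related adverse event, plus up to 7 for logistics (Protocol 6.2.1.4.1).

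**Reproducing the documents' own figures**

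The SAP prints no numerical result of the duration rule, so the check starts from the schedule.

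- Day of pembrolizumab cycle 35: 15 + 34 × 21 = 729 and 19 + 34 × 21 = 733, as in Tables 7-2 and 7-4.
- Planned blinatumomab days at target dose: 56 − 7 = 49, 56 − 14 = 42, 28 − 7 = 21 and 28 − 14 = 14, as in SAP 6.1.

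**Pembrolizumab under the SAP rule**

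Within a cycle, last date = first date, so duration = 0 + 1 = 1 day, and the sum over n cycles is n days. The first-to-last-dose span is (n − 1) × 21 + 1 days.

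| Cycles given | SAP rule (days) | First-to-last span (days) | Ratio |
|---|---|---|---|
| 1 | 1 | 1 | 1 |
| 2 | 2 | 22 | 11 |
| 5 | 5 | 85 | 17 |
| 35 | 35 | 715 | 20.4 |

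The 715 days agree with the schedule: 729 − 15 + 1 = 733 − 19 + 1 = 715. Using the episode rule instead does not help, since 35 × 30 / 1440 = 0.73 day.

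**Blinatumomab cycle 1 under the SAP rule**

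Assume 56 days are infused in total, with one gap of g days. An infusion begun during day 1 ends on calendar day 56 + g + 1, so last − first + 1 = 57 + g.

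| Gap (days) | SAP rule (days) | Days infused | Excess |
|---|---|---|---|
| 0 | 57 | 56 | 1 (1.8%) |
| 7 | 64 | 56 | 8 (14.3%) |
| 14 | 71 | 56 | 15 (26.8%) |
| 21 | 78 | 56 | 22 (39.3%) |

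If the last full infusion day is taken as the last date, each result is 1 day lower: 70 days for the 14-day gap, an excess of 14 / 56 = 25%.

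**The case against.** A reader might infer that the rule is wrong for both drugs, that the SAP contradicts itself within one entry, and that poorly tolerated cohorts would look better exposed than they were. The documents do not support any of these.

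- **Duration of therapy is not exposure.** SAP 10.6.8 plans duration of therapy. For a continuous infusion, a first-to-last-date span within a cycle is a usable definition, and it is at most 1 day high when nothing is interrupted.
- **The two levels can serve different outputs.** SAP 6.1 calls the episode quantity exposure, and its cumulative-dose definition needs an infusion duration for each dose received. The episode rule therefore has an evident use of its own. What remains is unclear labelling.
- **Poor tolerance would be visible elsewhere.** SAP 10.6.8 also reports cycles started, completed, discontinued and restarted (completion requires 85% of planned target-dose days), relative dose intensity at target dose, and interruptions with reasons.
- **The blinatumomab size is illustrative.** The documents give no expected frequency or length of interruptions. The 14-day case takes the adverse-event limit and assumes that all 56 infusion days are still delivered.

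For pembrolizumab it can be said that 35 cycles is the maximum, and that a reader can roughly recover treatment length from the tabulated cycle counts. Both are true, but neither makes the reported duration correct: at 5 cycles it is still 5 days against 85. It can also be said that a first-to-last span for pembrolizumab would include time when doses were withheld. That is acceptable for a duration of therapy, on the same footing as the blinatumomab span, if the number of infusions stands beside it.

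**Conclusion.** The pembrolizumab half stands as written. The rule returns the number of infusions: 35 days at 35 cycles against a 715-day span, about 20-fold too low. The ratio grows with cycles given and is 1 for a subject with a single infusion. This rests on one infusion date per cycle and on-schedule dosing; a shift of up to 3 days per dose, which the protocol permits, barely changes it.

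The blinatumomab half is a matter of labelling. The span includes interruption days, about 70 to 71 days for 56 infused with a 14-day gap. It is sound as elapsed time and misleading only if read as time on drug.

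The consequence is small. Only descriptive exposure tables are affected. DLT incidence, the MTD and ORR do not use this rule. The treatment period and the treatment-emergent window run from last dose or end of treatment plus 30 days, not from this duration.

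**What to change.** In SAP 6.1, split the entry by drug:

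- **Pembrolizumab:** overall duration of therapy = last infusion date − first infusion date + 1, with the number of infusions reported alongside. Drop the by-cycle duration, which carries no information, and amend SAP 10.6.8 to match.
- **Blinatumomab:** keep last − first + 1 per cycle, labelled as elapsed time on therapy. Report separately, as exposure, the sum of infusion-episode durations under the SAP's existing date-and-time rule. Rounding to the nearest day then has a purpose.

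It would help to add one clause saying that the actual exposure at target dose in relative dose intensity uses the episode durations, since the SAP does not say how it is computed.

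The cost is a few lines of SAP text and a minor change to table specifications. Protocol 6.2.1.1 already requires start and stop dates and times on the case report form, so no new data are needed.

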^h Report AEs occurring after enrollment **through the last safety follow-up visit that occurs 30 days (+7 days) following cessation of treatment. Report SAEs that occur after signing of the informed consent form through 90 days following cessation of treatment, or 30 days following cessation of treatment if the subject initiates new anticancer therapy, whichever is earlier. After this period, report SAEs suspected to be related to IP, and fatal SAEs regardless of causality.**

ⁱ Available results of brain contrast-enhanced MRI performed up to 8 weeks prior to first day of study treatment are acceptable. In case of neurologic AE ≥ grade 3 a brain MRI should be performed.

^j If PET scans and CT scans are done separately, they must be within the ± 3 day window and a maximum of 72 hours apart. If PET and CT are acquired on the same day, it is strongly recommended that PET is performed prior to the CT with IV contrast.

^k Enhanced MRI will be allowed to replace CT strictly when iodinated contrast is contraindicated.

^l After week 10 and during LTFU, subjects should have scans performed per the regular frequency every 12 weeks (± 3 days). PET/CTs should be performed until documented complete remission, progressive disease, or 24 months after the first assessment. Response assessment will also be conducted at the time of treatment discontinuation due to clinically suspected disease progression. In case of suspected pseudo-progression, repeat imaging performed 4 to 8 weeks from initial assessment suspicious for PD. Subjects who receive at least 1 full dose of pembrolizumab who discontinue from all study treatment in cycle 1, for whatever reason, shall undergo a PET/CT scan between 14 to 28 days after last pembrolizumab exposure.

^m Scans done within 28 days prior to first dose may be used in place of protocol-required assessments.

ⁿ If PET scan at Screening is negative for disease involvement in the neck, screening and subsequent CT scans may not include neck. If PET scan at Screening is positive for disease involvement of the neck, subsequent CT scans must include neck.

^o For lymphomas that are not FDG-avid at screening, PET does not need to be repeated in follow-up assessments.

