7.2.2 Treatment

The following procedures will be completed during the treatment period at the times designated in the Schedule of Assessments ([Table 7-1](#), [Table 7-2](#), [Table 7-3](#), and [Table 7-4](#)). Administration of protocol-required therapies is to be administered last during each visit that it is required.

- Physical Examination
- PK (including intensive PK assessments)
- Vital signs (eg, blood pressure, heart rate, respiration rate, temperature)
- Laboratory Assessments including local and central laboratories, as applicable
- Imaging Assessments
- Serious Adverse Event reporting
- Adverse Event reporting
- Disease Related Event Reporting
- Documentation of concomitant medications
- Receipt of protocol-required therapies

If a subject stops treatment (eg, due to an adverse event), the investigator must ensure there is a plan for continued follow-up until the subject completes all protocol-required visits or withdraws from the study.

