7.3.12.3 Timing of Disease Assessments

Uniform disease response assessments will occur initially at 10 weeks (D64) (± 3 days) after treatment start of blinatumomab and thereafter every 12 weeks (± 3 days). **The scan on Day 64 will be compared to the scan from screening. Any other scan thereafter will be compared to the scan that was done immediately before it.**

PET/CT should be performed until documented complete remission, PD, **or relapse** or 24 months after the first assessment. Response assessment will also be conducted at the time of treatment discontinuation due to clinically suspected disease progression **or relapse**. If PET scans and CT scans are done separately, they both must be within the ± 3 -day window and a maximum of 72 hours apart. If PET and CT are acquired on the same day, it is strongly recommended that PET is performed prior to the CT with IV contrast. Subjects who receive at least 1 full dose of pembrolizumab who discontinue from all study treatment in cycle 1, for whatever reason, shall undergo a PET/CT scan between 14 to 28 days after last pembrolizumab exposure.

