7.3.12.4 Disease Assessments During the Trial

Immunotherapeutic agents such as pembrolizumab may produce antitumor effects by potentiating endogenous cancer-specific immune responses, which may be functionally anergic. The response patterns seen with such an approach may extend beyond the typical time course of responses seen with cytotoxic agents, and can manifest a clinical response after an initial increase in tumor burden or even the appearance of new lesions. Standard response assessment criteria may not provide a comprehensive response assessment of immunotherapeutic agents such as pembrolizumab.

In the setting where a subject's assessment shows unconfirmed PD/**relapse** by investigator assessment, study drug may be continued upon sponsor consultation if the

investigator considers the subject is clinically stable, and repeat imaging performed in 4-8 weeks from initial assessment suspicious for PD/**relapse**. Subjects that remain on treatment after the first suspicion of progression/**relapse** who then become clinically unstable are not required to have repeat imaging for confirmation.

Clinical Stability may be defined as:

- Absence of signs and symptoms (including worsening of laboratory values) indicating disease progression
- No decline in ECOG performance status
- Absence of rapid progression of disease or progressive tumor at critical anatomical sites (eg, cord compression) requiring urgent alternative medical intervention.

Imaging should also occur at any time when there is clinical suspicion of progression/**relapse**. If repeat imaging shows a reduction or stabilization in the tumor burden compared to the initial scan demonstrating PD, treatment may be continued/resumed. If repeat imaging confirms PD by investigator assessments, subjects will be discontinued from study therapy.

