10.4.2.2 Secondary Efficacy Endpoints

The percentage of subjects with an objective response using the Lugano Classification and Revised Response Criteria during 12 weeks since starting blinatumomab will be summarized with an exact 2-sided binomial 95% confidence interval, respectively. The percentage of subjects with an objective response using the Lugano Classification during the entire treatment period will also be summarized. Subjects missing post baseline disease assessments will be considered not to have achieved an objective response.

The KM summaries will be performed for PFS, OS, and DOR.

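### The SAP's treatment period can close before the D64 scan, so an early stopper who responds at D64 is a 12-week responder but a treatment-period non-responder

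*SAP*

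**What the plan says.** - **Definition.** SAP 6.1 ends the period 30 days after the last dose: "Treatment period will be from study day 1 to 30 days after last dose of either blinatumomab/ pembrolizumab". There is no separate definition for efficacy. SAP 4.1.2, 6.2 and 10.5 use this period for objective and complete response, beside a window covering the first 12 weeks of blinatumomab.
- **Protocol wording.** Protocol 10.4.2.2 says that "an objective response using the Lugano Classification during the entire treatment period will also be summarized" and gives no dates, so the 30-day limit comes from the SAP.
- **Scans.** Protocol 7.3.12.3: "Uniform disease response assessments will occur initially at 10 weeks (D64) (± 3 days) after treatment start of blinatumomab and thereafter every 12 weeks". Scanning does not stop with treatment. The footnotes to Table 7-1 say "After week 10 and during LTFU, subjects should have scans performed per the regular frequency every 12 weeks" and "PET/CTs should be performed until documented complete remission, progressive disease, or 24 months after the first assessment". Protocol 7.2.2 adds that after stopping treatment "the investigator must ensure there is a plan for continued follow-up until the subject completes all protocol-required visits or withdraws from the study".
- **Extra scan.** Protocol 7.3.12.3 also requires a PET/CT 14 to 28 days after the last pembrolizumab exposure for subjects who had at least one full dose and stop all treatment in cycle 1.
- **Populations.** The Full Analysis Set is everyone who received blinatumomab (SAP 7.1). The Responder Analysis Set, used for duration of response, is the 12-week responders (SAP 7.3, 10.5). By its wording, SAP 10.5 appears to limit the 12-week rate to part 2 and the selected part 1 cohort. SAP section 11 records that part 2 will not go ahead.

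**The concern.** A 30-day tail is the usual reporting window for adverse events, and the SAP uses the same tail for treatment-emergent events. Applied to response, it can close before the first scheduled scan. A reader who sees one response rate for the first 12 weeks and another for the whole treatment period will expect the second to be at least as high as the first. Under this definition it need not be. The same subject could be in the Responder Analysis Set and contribute to duration of response, yet be a non-responder for the treatment period. If the 12-week rate is reported only for a selected cohort, such a response in another cohort may enter no summarised response rate. The protocol itself expects that responses to this class "may extend beyond the typical time course of responses seen with cytotoxic agents", so a first response at D64 after early stopping is not far-fetched.

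**Working it through.** This is day arithmetic.

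**Inputs.** Period end = last dose day L + 30 (SAP 6.1). Scheduled scans at 64 + 84k, each ±3 days (Protocol 7.3.12.3). First pembrolizumab dose on D15 (cohort Ia) or D19 (cohorts IIa and IIIa), then every 21 days (Tables 7-2 and 7-4).

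**1. Check against the protocol's own days.** Pembrolizumab cycle 35 falls on 15 + 21 × 34 = 729, and 729 + 30 = 759. For the other cohorts, 19 + 21 × 34 = 733, and 733 + 30 = 763. Both match the safety follow-up days in Tables 7-2 and 7-4. For a full course every scheduled scan from D64 to D736 is counted.

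**2. When D64 drops out.** A scan on day S counts if S ≤ L + 30, so it is excluded if L ≤ S − 31.

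| Actual day of the D64 scan | Excluded if last dose is on or before |
|---|---|
| D61 | D30 |
| D64 | D33 |
| D67 | D36 |

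The treatment period covers all of day 1 to day 84 only if L ≥ 84 − 30 = 54.

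**3. Who is affected (nominal days).**
- Last dose D14, no pembrolizumab: the period ends on 14 + 30 = D44. The extra scan is not required. A response at D64 counts for 12 weeks and not for the treatment period.
- One pembrolizumab dose on D15 or D19, all treatment stopped by D33: the extra scan falls on D29 to D43, or D33 to D47. The period ends no earlier than D45 or D49, so this scan always counts. A discrepancy remains only if PR, or an upgrade from PR to CR, is first seen at D64.
- Second pembrolizumab dose given on D36 or D40: the period reaches at least D66 or D70, so the nominal D64 scan counts.

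**4. Size.** One subject is 1/6 = 16.7 points in a cohort of 6 and 1/10 = 10.0 points in a cohort of 10.

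**5. The word *either*.** The treatment-emergent definitions in SAP 6.1 specify the later of the two drugs; the treatment-period definition does not. Read as blinatumomab alone, a subject finishing cycle 2 at D113 would have a period ending on 113 + 30 = D143. That is before the second scan (D145 to D151), although pembrolizumab may continue to D729 or D733.

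**The case against.** The strongest reply is that an on-treatment response rate with a 30-day tail is a legitimate endpoint, and that neither document says the treatment period must contain the first 12 weeks. The 12-week endpoint captures D64 whenever treatment stopped. The efficacy stopping rule uses 12-week response, duration of response uses 12-week responders, and PFS and OS do not depend on this period. The extra 14-to-28-day scan already covers many early stoppers who had pembrolizumab. All of this stands, and it limits the point to a minor one. It does not remove the inconsistency: the SAP does not call the rate on-treatment, and the protocol speaks of the entire treatment period.

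Three stronger readings are tempting but not supported.
- A reader might infer that the 84-day scan spacing pulls the treatment-period rate below the 12-week rate. It cannot: the second scheduled scan, D148, is outside the 12-week window. The shortfall comes only from D64 combined with early stopping.
- A reader might infer that the first scan after consolidation never counts once pembrolizumab has stopped. If cycle 2 starts three days late and ends about D116, the period ends about D146, and a scan on D145 or D146 counts. If pembrolizumab continues, cycle 6 on D120 or D124 carries the period to D150 or D154, and the nominal D148 scan counts.
- A reader might infer that the next scan after stopping counts only 30/84 = 36% of the time. That assumes last doses spread evenly over all days. Once only pembrolizumab every 21 days remains, the candidate last doses before D232 in cohort Ia are D162, D183, D204 and D225. The last two reach D232 (204 + 30 = 234; 225 + 30 = 255), so 2 of 4.

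Scheduled scans more than 30 days after the last dose are indeed not counted, but for an on-treatment endpoint that may be intended.

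**Conclusion.** The point holds in a narrow form. As written, the SAP lets a D64 response count for 12 weeks but not for the treatment period when the last dose is on or before about D33 (D30 to D36 with the scan window). The treatment-period ORR or CR rate can then be below the 12-week rate in the same population. In cohorts for which no 12-week rate is reported, the response may appear in no summarised rate. Each such subject is worth 10 to 17 points in a cohort of 10 to 6. That is the effect of one subject, not an estimate of how likely it is: the documents do not give the frequency of stopping this early. The conclusion assumes that the D64 scan is done after stopping, as the protocol requires, and that *either* means the later drug. Severity is minor, because no stopping rule or test uses this rate.

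**What to change.** In SAP 6.1, add a definition for response endpoints only: the treatment period runs from study day 1 to the later of (a) 12 weeks after starting blinatumomab and (b) 30 days after the last dose of blinatumomab or pembrolizumab, whichever is later. This places the 12-week window inside the treatment period for every subject, so the treatment-period rate cannot be lower in the same population. It also removes the ambiguity of *either* and aligns the wording with the treatment-emergent definitions. Leave the safety windows unchanged.

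The cost is one sentence and no new data. Part (a) credits nothing that the 12-week endpoint does not already credit.

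Counting the first scheduled scan after the last dose is at most an optional sensitivity analysis. It would credit scans up to 84 + 3 = 87 days off drug, and Protocol 6.9 and 7.2.3 foresee new anti-lymphoma therapy even within 30 days. If done, it should exclude responses first seen after new anticancer therapy.
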